Randomized controlled trial comparing covered metal stents versus uncovered metal stents for palliative biliary decompression in inoperable malignant distal bile duct obstruction

Participating centers:

Vanderbilt University Medical Center

Principal Investigator:

[name] MPH

Version Date: September 23, 2019

Background:

Endoscopic retrograde cholangiopancreatography (ERCP) with transpapillary placement of an endoprosthesis is an established intervention for palliation of malignant distal extrahepatic bile duct obstruction. Such intervention may provide relief of jaundice and pruritus, reduce the risk of ascending cholangitis, and permit administration of systemic chemotherapy. Plastic biliary stents are prone to stent occlusion and malfunction, with median stent patency duration of 12 weeks for 8 French gauge stents and 32 weeks for 10 French gauge stents¹, and therefore require repeat intervention via ERCP for stent removal and exchange every several months. The need for repeat intervention may require interruption of ongoing chemotherapy, may be otherwise undesirable from a patient perspective, and may have cost implications. Indeed, the goal of endoscopic biliary decompression should be to provide durable biliary drainage—ideally extending for the duration of the patient’s overall survival—in a single intervention.

Self-expanding metal biliary stents (SEMS) offer an internal diameter up to 10 mm, offer more durable biliary drainage compared to plastic stents^{2,3}, and have therefore become the endoprosthesis of choice for palliation of inoperable malignant distal bile duct obstruction. Variations in SEMS design exist, however, and the choice of ideal SEMS is uncertain—uncovered SEMS (U-SEMS) consist of a bare metal scaffold which may be prone to hyperplastic tissue ingrowth and stent occlusion; alternatively, covered SEMS (C-SEMS) feature a polyurethane coating which may prevent tissue ingrowth but which may increase the likelihood of inadvertent stent migration. A prior randomized controlled trial of a stainless steel U-SEMS versus a stainless steel partially covered C-SEMS revealed no difference in time to recurrent biliary obstruction⁴; and a recent meta-analysis demonstrated no clear advantage of C-SEMS vs U-SEMS⁵.

Due to variations in stent material, design, and manufacture, however, such data may not be generalizable to current generation metal stents, which feature a nickel titanium alloy scaffold and which, in C-SEMS version, offer a full rather than partial polyurethane coating.

Hypothesis:

We hypothesize that current generation C-SEMS offer more durable biliary drainage and will decrease the need for biliary reintervention compared to U-SEMS in patients with inoperable malignant distal bile duct obstruction.

Objectives:

Primary objective: Compare the rate of long-term stent failure, defined as need for repeat biliary intervention (endoscopic, percutaneous, or surgical) following placement of C-SEMS vs U-SEMS for palliation of inoperable malignant distal bile duct obstruction.

Secondary objective: Compare the rate of adverse stent-related or intervention-related outcomes (pancreatitis, cholangitis, cholecystitis, perforation) following placement of C-SEMS vs U-SEMS for palliation of inoperable malignant distal bile duct obstruction.

Design:

Single-center prospective randomized controlled trial.

Inclusion criteria:

- Patients with distal bile duct obstruction due to pancreatic cancer, cholangiocarcinoma, or metastatic malignancy with a confirmed tissue diagnosis referred for ERCP with intended palliative metal stent placement for palliation of jaundice
- Patients 18 years of age and older
- Serum bilirubin > 2 mg/dL

Exclusion criteria:

- Prior endoscopic or percutaneous biliary drainage
- Post-surgical anatomy (ie pancreaticoduodenectomy, Billroth-type gastrectomy, Roux-en Y hepaticojejunostomy)
- Primary site of biliary obstruction involving the common hepatic duct or hilum
- Tumor involving gastric outlet, duodenum, or ampulla either precluding endoscopic access to the papilla or otherwise preventing endoscopic biliary cannulation
- Inability to provide written informed consent

Procedure:

- Patients will undergo ERCP under either MAC/general anesthesia or conscious sedation per institutional standard of care.
- Following endoscopic biliary cannulation and diagnostic cholangiography, performed per standard of care, a sealed envelope will be opened to determine patient randomization to either a 10 mm diameter C-SEMS (Wallflex, Boston Scientific) or a 10 mm diameter U-SEMS (Wallflex, Boston Scientific). Due to the nature of the intervention, the proceduralist will not be blinded to study allocation. The choice of a 40 mm or 60 mm stent length will be at the discretion of the proceduralist.
- Post-procedure monitoring and discharge will be performed per institutional standard of care.

Follow-up:

- Day 1 follow-up for assessment of post-procedural adverse events will be performed by telephone call by an endoscopy post-assessment nurse (for outpatients) or by physician assessment at the patient's bedside (for inpatients), as per current institutional standard of care
- Follow-up will occur every 60 days by review of the electronic medical record or patient self-report to assess for primary and secondary study outcomes

Major treatment outcomes:

- Primary outcome: Performance of repeat ERCP, percutaneous biliary drainage, or surgical biliary bypass for palliation of persistent or recurrent biliary obstruction.
- Secondary outcomes: pancreatitis requiring hospital admission; cholangitis requiring hospital admission and intravenous antibiotics; cholecystitis requiring percutaneous, surgical, or endoscopic intervention; perforation.

Sample size and planned statistical analysis:

Retrospective data from VUMC has identified a long-term 25% failure rate of U-SEMS and 0% failure rate of C-SEMS when placed for palliation of malignant distal bile duct obstruction⁶. Assuming a somewhat more conservative estimate of durability rates, a sample size of 96 patients (48 per treatment arm) would be required to detect a 20% difference in stent failure rates at 80% power with an alpha level of 0.05. Also anticipating a 20% rate of dropout/loss to follow-up, the goal would be to enroll and randomize 116 total patients in the study.

Fisher's exact test will be used to assess the statistical significance in proportion of primary and secondary study outcomes, respectively. Additional univariate and multiple variable logistic regression analysis will be used to identify potential predictors of stent failure, to be reported including odds ratio and 95% confidence intervals. A two-sided P value of <0.05 will be the threshold for statistical significance in all cases.

Role of industry:

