Appendix A—Data Instrument

Study ID: _____

Demographics:

Age_____ Gender: M F

Underlying diagnosis:

Pancreatic CA Cholangio CA Other (specify)_____

Additional clinic data:

Serum bilirubin (mg/dL) _____

Serum WBC_____

Prior cholecystectomy Y N

Cholangiographic and technical procedure data:

Stricture length at ERCP: _____cm

Stricture extending to ampulla: Y N

Endoscopic ampullary mass present: Y N

Stricture involving cystic duct takeoff Y N indeterminate

Randomization: C-SEMS U-SEMS

Follow-up:

Day 1 adverse events: pancreatitis cholangitis cholecystitis perforation none

Day 30 (and at each 30 day interval thereafter):

Patient alive: Y N If deceased, days from stent placement until death: ____

Repeat ERCP since stent placement: Y N

Percutaneous biliary drainage since stent placement: Y N

Surgical biliary bypass since stent placement: Y N

Surgical, endoscopic, or percutaneous gallbladder interventi

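### The envelope may be opened before it is known that a study stent can be placed, and the plan does not settle how a randomized patient without a stent is counted

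*Combined protocol and SAP*

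**What the plan says.** The Procedure section states: "Following endoscopic biliary cannulation and diagnostic cholangiography, performed per standard of care, a sealed envelope will be opened to determine patient randomization". The same bullet says that the proceduralist is not blinded to allocation.

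The Exclusion criteria remove tumor "either precluding endoscopic access to the papilla or otherwise preventing endoscopic biliary cannulation". They also remove primary obstruction at the common hepatic duct or hilum. A stricture that can be cannulated but not crossed is not listed.

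Three places bear on whether a randomized patient without a stent can have a primary event:

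- Major treatment outcomes: "Performance of repeat ERCP, percutaneous biliary drainage, or surgical biliary bypass for palliation of persistent or recurrent biliary obstruction"
- Objectives section, first statement: "Compare the rate of long-term stent failure, defined as need for repeat biliary intervention (endoscopic, percutaneous, or surgical) following placement of C-SEMS vs U-SEMS"
- Appendix A, follow-up items: "Repeat ERCP since stent placement: Y N"

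The Sample size section gives the historical basis: "Retrospective data from VUMC has identified a long-term 25% failure rate of U-SEMS and 0% failure rate of C-SEMS". It then adopts an unstated, more conservative pair of rates with a 20-point difference, 48 patients per arm, 80% power and two-sided alpha 0.05. The test is Fisher's exact test. No analysis population is defined. As far as the Appendix A form can be read, it has no item for crossing of the stricture or for successful stent placement.

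**The concern.** Cannulation and cholangiography are the only steps that must come before allocation. If the stricture then cannot be crossed, the patient is randomized, has no study stent, and will probably need another drainage procedure. That procedure says nothing about covered versus uncovered mesh. The same gap applies to the hilar exclusion: it may become clear only on the cholangiogram, yet nothing requires it to be checked off before the envelope is opened.

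The plan then allows two treatments of such a patient. If never-relieved obstruction counts as persistent obstruction, the patient is an event. Events of this kind occur at the same rate in both arms, shrink the difference and add variance. If failure is counted only after a stent has been placed, the patient has no starting point and drops out of the comparison. In that case randomized patients are removed on the basis of what an unblinded proceduralist did after learning the allocation. Neither route is chosen in the plan, and the choice could be made after results are known.

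**Working it through.** **Inputs from the plan.** 48 per arm, 20-point difference, 80% power, two-sided alpha 0.05, Fisher's exact test; historical failure rates 25% (uncovered) and 0% (covered).

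**Assumed inputs.** (a) Placed-stent failure rates of 25% v 5%, because the plan gives only the difference. (b) A share t of randomized patients, equal in both arms, whose stricture is not crossed; t = 1% to 5% is a range for illustration, as the documents give none. (c) Every such patient is drained again and counts as an event.

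**Step 1: the plan's own figure.** For 25% v 5%, with pooled variance under the null and mean rate 0.15:

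n = [1.960 × √(2 × 0.15 × 0.85) + 0.842 × √(0.25 × 0.75 + 0.05 × 0.95)]² / 0.20² = (0.990 + 0.408)² / 0.04 ≈ 48.8, so 49 per arm.

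The plan has 48, so the assumed pair is a reasonable reading. At 48 per arm the normal approximation gives 79.3% power. Exact Fisher power, by enumerating all outcomes, is 72.2%. That gap of about 7 points exists before any failed crossing and is a separate matter.

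**Step 2: dilution.** If failed crossings count as events, each arm's rate becomes p′ = t + (1 − t)p.

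| t | Rates from 25% v 5% | Difference | Fisher power, 48/48 | Rates from 25% v 0% | Fisher power, 48/48 |
|---|---|---|---|---|---|
| 0 | 25.0% v 5.0% | 20.0 | 72% | 25.0% v 0% | 99% |
| 1% | 25.75% v 5.95% | 19.8 | 69% | 25.75% v 1% | 96% |
| 2% | 26.5% v 6.9% | 19.6 | 66% | 26.5% v 2% | 94% |
| 3% | 27.25% v 7.85% | 19.4 | 63% | 27.25% v 3% | 91% |
| 5% | 28.75% v 9.75% | 19.0 | 57% | 28.75% v 5% | 85% |

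**Step 3: where the loss comes from.** At t = 5% the difference shrinks by 5% (20.0 to 19.0 points). Its standard error rises from √(0.235/48) = 0.0700 to √(0.293/48) = 0.0781, about 12%. Most of the loss is therefore added variance, as the covered arm's rate nearly doubles.

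**Step 4: the other reading.** If these patients are left out, the rates stay at 25% v 5% and only the count falls. At t = 5%, 48 × 0.95 = 45.6, so about 46 per arm. Fisher power is 72.1% at 46/46 against 72.2% at 48/48. Almost no power is lost; the cost is the post-randomization exclusion.

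**Step 5: how many patients.** Among 96 analyzed, 1% to 5% is about 1 to 5 patients.

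**The case against.** The other side has several fair points.

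- **A reader might infer that the envelope is always opened before crossing is known.** The documents do not say so. They neither require nor rule out crossing first, and the reference to standard of care leaves it open. Appendix A lists "Stricture length at ERCP: _____cm" above the randomization item, which suggests that the stricture is delineated first, though it does not show that a wire has passed. What stands is the absence of a requirement.
- **A reader might infer that failed crossings definitely count as primary events.** The objective and the form tie events to stent placement, and persistent obstruction can also describe a placed stent that never drains. The text supports only that they can count.
- **A reader might infer that the planning rates leave out technical failures.** The plan attaches placement to the historical figures: "0% failure rate of C-SEMS when placed for palliation of malignant distal bile duct obstruction". The planning rates are separate and unstated, and their margin may already allow for some technical failure.
- **The size is fragile.** Under 25% v 5%, moving from 47/47 to 47 uncovered and 48 covered shifts Fisher power from 70.8% to 78.6%. That is more than the effect of a 1% or 2% failed-crossing rate.
- **Randomization is already late.** Failed cannulation comes before the envelope, and failed access and hilar disease are excluded. A prespecified analysis of patients with a stent placed could also be argued for, since crossing is the same task in both arms.

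The first four points limit how strongly the concern can be put. The last does not remove it: no such population is specified, and in an open-label procedure a stent-placed population depends on decisions made after allocation is known.

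**Conclusion.** The concern holds in a limited form. The plan does not ensure that a study stent can be placed before allocation is revealed, and it gives conflicting signals on how a randomized patient without one is counted.

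Under the assumptions in the working (25% v 5%, equal failed crossing in both arms, all counted as events), the attributable loss in exact power is about 3 points at a 1% failed-crossing rate, 7 at 2% and 15 at 5%. At small rates, most of the gap below 80% comes from the conservatism of Fisher's test. Under the historical 25% v 0%, power stays at 85% or more up to 5%. So it would be wrong to conclude that the timing of the envelope by itself leaves the trial underpowered.

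It would also be wrong to conclude that it favors one stent. Failures that precede stent choice and are equal between arms cost power and favor neither. A risk of bias arises only if such patients are dropped after allocation is known, and the documents do not allow its size to be estimated. The change is worth making because it is cheap and closes both routes.

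**What to change.** 1. Add to the Procedure bullet: *The envelope is opened only after a guidewire has crossed the stricture and the cholangiogram has confirmed that no exclusion criterion applies, including common hepatic duct or hilar obstruction. Patients who do not reach this point are logged as screened and not randomized.*
2. State in the analysis section that all randomized patients are analyzed in the arm to which they were allocated.
3. Reconcile the primary objective and the Appendix A items, which count from stent placement, with the primary outcome, which covers persistent as well as recurrent obstruction. One rule should say how a randomized patient without a stent is counted.
4. Add to the data form a tick-box for crossing and eligibility above the randomization item, and a field for whether the allocated stent was placed.

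The cost is a few sentences and two form items. Slightly more patients must be screened, and the results apply to patients whose stricture can be crossed. If crossing already comes before the envelope in practice, the first change only records what is done.

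### Each follow-up may rest on the medical record or self-report alone, so a reintervention or admission at another hospital can be recorded as 'no'

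*Combined protocol and SAP*

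**What the plan says.** The Follow-up section describes direct contact at day 1, by telephone or at the bedside. After that, "Follow-up will occur every 60 days", "by review of the electronic medical record or patient self-report", and this covers the primary and the secondary outcomes alike. No sentence requires the patient to be asked when the record is silent, or requires records from other hospitals.

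The Design section describes a "Single-center prospective randomized controlled trial". The Inclusion criteria admit patients "referred for ERCP with intended palliative metal stent placement for palliation of jaundice".

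Under Major treatment outcomes, the primary outcome is "Performance of repeat ERCP, percutaneous biliary drainage, or surgical biliary bypass for palliation of persistent or recurrent biliary obstruction". It is not limited to procedures at the study hospital. The secondary outcomes include "pancreatitis requiring hospital admission; cholangitis requiring hospital admission and intravenous antibiotics", again wherever the admission takes place.

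In Appendix A, the items on repeat ERCP, percutaneous drainage and surgical bypass are cumulative from stent placement and are answered yes or no. The text of the form breaks off at the gallbladder item, so nothing can be said about later fields. The form is headed "Day 30 (and at each 30 day interval thereafter", which differs from the 60-day interval in the Follow-up section. That mismatch is a separate point, to be reconciled when the section is revised.

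The sample size section anticipates 20% dropout or loss to follow-up. The plan does not say when a patient with a silent record counts as lost and when as event-free.

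**The concern.** The primary endpoint is the occurrence of a procedure, and the planned analysis compares proportions. An event that nobody finds does not appear as a missing value; it enters the Fisher test as a stent that lasted. The same holds for admissions for pancreatitis or cholangitis after day 1.

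The plan permits this outcome. A coordinator who reviews only the center's record, finds no procedure and circles 'N' has followed the protocol. With one center and patients referred for a procedure, some later care at other hospitals is plausible, although its extent is not stated.

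The trial expects few failures, so a handful of missed events matters. Under 25% v 5% with 48 per arm, the expected number is 48 × 0.25 + 48 × 0.05 = 12 + 2.4 = 14.4. Missing 10% to 20% of these is a loss of about 1.4 to 2.9 events in the whole trial.

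**Working it through.** **Inputs from the documents** (Sample size and planned statistical analysis): a 20-point difference, 80% power, two-sided alpha 0.05, 48 evaluable per arm, 20% loss, 116 randomized (58 per arm), Fisher's exact test.

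**Assumed inputs:** the per-arm planning rates are not stated. I use 25% v 5%, with 20% v 0% as the alternative. The share m of events missed is not given either. I use 10% and 20%, equal in both arms.

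**Step 1: the plan's own figure.** For p₁ = 0.25, p₂ = 0.05 and mean 0.15, the usual formula is

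n = [1.96·√(2·0.15·0.85) + 0.8416·√(0.25·0.75 + 0.05·0.95)]² / 0.20² = (0.990 + 0.408)² / 0.04 ≈ 48.8, so 49 per arm.

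With unpooled variance, n = 0.235 × (1.96 + 0.8416)² / 0.04 ≈ 46.1, so 47 per arm. The stated 48 lies between them, so 25% v 5% is a reasonable reading of the plan. The 116 is 96 × 1.2 = 115.2, rounded up.

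**Step 2: what is observed when events are missed.** Observed rate = true rate × (1 − m).
- m = 10%: 0.25 × 0.9 = 22.5% and 0.05 × 0.9 = 4.5%, a difference of 18 points.
- m = 20%: 0.25 × 0.8 = 20% and 0.05 × 0.8 = 4%, a difference of 16 points.

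The ratio of the two rates stays at 5. The difference shrinks by the factor (1 − m).

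**Step 3: exact Fisher power.** This is the sum, over all pairs of event counts (a, b), of Bin(a; n, p₁) × Bin(b; n, p₂) for those pairs whose two-sided Fisher P is below 0.05.

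| True rates | n per arm | m = 0 | m = 10% | m = 20% |
|---|---|---|---|---|
| 25% v 5% | 48 | 72.2% | 64.9% | 56.6% |
| 25% v 5% | 58 | 82.9% | 76.9% | 69.4% |
| 20% v 0% | 48 | 93.8% | 88.5% | 80.1% |
| 20% v 0% | 58 | 98.4% | 96.2% | 91.9% |

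The rows with 58 per arm matter because patients with a silent record who are kept as event-free have not been lost. In that case up to all 116 are analysed.

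**Step 4: type I error and bias.** If the true rates are equal, equal m leaves the observed rates equal, so the level of the test is unaffected. Unequal m can move the difference either way. Under 25% v 5%:
- Missing 30% in the uncovered arm and 10% in the covered arm gives 17.5% − 4.5% = 13 points.
- Missing none in the uncovered arm and 30% in the covered arm gives 25% − 3.5% = 21.5 points.

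Nothing in the documents indicates that either pattern would occur.

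**The case against.** The strongest reply is that permission is not practice. Staff may well use self-report wherever the record is silent, and the record may contain outside documents. The form items run from stent placement, so an event missed at one check can be picked up at the next. The form also asks whether the patient is alive, which a silent record does not answer. Day 1 events are covered by direct contact, and 20% loss is anticipated. These points reduce the likely number of missed events. They do not close the gap, because none of them requires anyone to ask the patient when the record shows nothing, and the day 1 contact covers only immediate events.

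Several stronger readings are tempting and should not be drawn:
- **That outside events will be coded as 'no'.** The plan allows this; it does not instruct it. Because the form text is incomplete, the lack of a later 'unknown' or lost-to-follow-up field cannot be held against the plan.
- **That the comparison between arms is biased.** A chance imbalance in where patients receive care is random error. Bias needs a systematic difference in under-recording, and the documents show none.
- **That ascertainment explains the 72%.** That baseline already lies below 80% with nothing missed. It comes from applying Fisher's test to a sample size close to the approximate formula, which is a separate matter.
- **That 65% and 57% are the expected power.** They are the low end of a range that depends on the unstated planning rates and on how many patients are analysed. The 25% for uncovered stents also comes from retrospective data at the same center. If it was drawn from that center's records, it may already reflect some missed events.
- **That referral shows outside care is common.** Referral can be internal.

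**Conclusion.** The concern holds as a gap in the ascertainment rule. Following the Follow-up section to the letter can turn a reintervention or admission elsewhere into a recorded non-event, for the primary outcome and for secondary outcomes after day 1.

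The size of the effect is unknown. Under the assumed 10% to 20% missed equally in both arms, the observed difference falls from 20 points to 18 or 16. Under 25% v 5%, power falls by about 7 or 16 percentage points at 48 per arm and by about 6 or 14 at 58 per arm. Under 20% v 0% at 48 per arm it falls by about 5 or 14 points but stays at or above 80%. The consequence is dilution and loss of power. False-positive risk does not rise, and no direction of bias between arms is established. The correction is cheap and protects the endpoint on which the conclusion rests, so it is worth making.

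**What to change.** In the Follow-up section, replace 'or' with 'and': each follow-up uses record review and patient or family report, by telephone if needed, with a direct question about procedures or admissions at other hospitals. Ask at every follow-up, not only when the record shows no encounter; a patient seen locally for another reason may still have been re-stented elsewhere.

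In Appendix A, add an 'unknown' code to the reintervention items.

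In the analysis section, state that a patient without a recorded event whose status could not be confirmed is counted in the anticipated loss to follow-up for the Fisher analysis. Add a sensitivity analysis that counts such patients as event-free. The pair is needed because only patients without a recorded event can be excluded under this rule, which tends to raise the failure proportions.

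The cost is some coordinator calls, using a source the plan already allows, and a less favourable completeness figure. Where calls fail, the analysed number moves from 58 towards 48 per arm. Under 25% v 5%, power at 48 with nothing missed (72%) is below power at 58 with 10% missed (77%). The change is therefore justified by correct outcome recording and not by a promised gain in power. Treatment, eligibility and the planned sample size are unaffected.

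### The 80% power at 48 per arm is given without the two failure rates or the sizing method; at the best-supported pair, 25% vs 5%, the planned two-sided Fisher's exact test has about 72%

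*Combined protocol and SAP*

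**What the plan says.** Everything relevant is in the section on sample size and planned statistical analysis.

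- Background rates: "Retrospective data from VUMC has identified a long-term 25% failure rate of U-SEMS and 0% failure rate of C-SEMS".
- Design assumption: "Assuming a somewhat more conservative estimate of durability rates". The estimate itself is not given.
- Size: "a sample size of 96 patients (48 per treatment arm) would be required to detect a 20% difference in stent failure rates", with 80% power and alpha 0.05.
- Dropout: "anticipating a 20% rate of dropout/loss to follow-up, the goal would be to enroll and randomize 116 total patients in the study".
- Test: Fisher's "exact test will be used to assess the statistical significance in proportion of primary and secondary study outcomes".
- Threshold: "A two-sided P value of <0.05 will be the threshold for statistical significance in all cases".

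No other part of the document gives the design rates or the formula used.

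**The concern.** Power for comparing two proportions depends on both rates, not only on their difference. The section starts from 25% and 0%, moves to an unspecified pair 20 points apart, and reports 48 per arm. A reader cannot confirm that 48 per arm gives the named test 80% power.

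The method matters as well. Common formulas for two proportions approximate the uncorrected chi-square test. Fisher's exact test is more conservative, noticeably so when one failure rate is near zero. If the trial was sized with such a formula and is analysed with Fisher's test, its real power is below the stated figure. A non-significant primary result would then be read as coming from a trial with a 20% risk of missing the effect, when the risk is larger.

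**Working it through.** **Inputs from the plan.** 48 per arm; a 20% difference, read as 20 percentage points; 80% power; two-sided alpha 0.05; Fisher's exact test; 116 randomized; 20% dropout.

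**Assumed input.** Design rates of 25% (U-SEMS) and 5% (C-SEMS). This keeps the only U-SEMS rate in the document, relaxes the C-SEMS rate from 0% to 5%, and gives the stated 20 points. Other 20-point pairs are shown below.

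**Step 1: reproduce the plan's 48.** The uncorrected two-sided formula, with mean rate p̄ = (0.25 + 0.05)/2 = 0.15, is

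n = [1.960·√(2·p̄(1 − p̄)) + 0.842·√(p₁(1 − p₁) + p₂(1 − p₂))]² / (p₁ − p₂)²

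- First term: 1.960 × √0.255 = 0.990
- Second term: 0.842 × √(0.1875 + 0.0475) = 0.842 × √0.235 = 0.408
- n = (0.990 + 0.408)² / 0.04 = 48.8 per arm

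By the same formula, power at 48 per arm is 79.3%. This is close to the plan, although rounding up would give 49. The formula gives about 42 per arm at 22.5% vs 2.5% and 35 at 20% vs 0%, so those pairs do not lead to 48 by this route. With a two-sided continuity correction, 25% vs 5% needs 58.4 per arm.

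**Step 2: power of the planned test.** For every possible pair of failure counts (i, j), compute the two-sided Fisher P value, and add up the binomial probabilities of the pairs with P < 0.05:

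power = Σ Bin(i; 48, p₁) · Bin(j; 48, p₂) · 1[P(i, j) < 0.05]

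| U-SEMS vs C-SEMS failure | Fisher power, 48 per arm |
|---|---|
| 20% vs 0% | 93.8% |
| 21% vs 1% | 88.0% |
| 22% vs 2% | 83.0% |
| 22.5% vs 2.5% | 80.8% |
| 23% vs 3% | 78.8% |
| 24% vs 4% | 75.3% |
| 25% vs 5% | 72.2% |
| 30% vs 10% | 61.3% |

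With the gap held at 20 points, power crosses 80% at a C-SEMS rate of about 2.7%.

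**Step 3: 25% vs 5% at other evaluable numbers.** 116 × 0.80 = 92.8, or about 46 per arm after the anticipated dropout.

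| Evaluable per arm | Fisher power |
|---|---|
| 46 (after 20% dropout) | 72.1% |
| 48 (the plan's target) | 72.2% |
| 55 (smallest giving 80%) | 80.1% |
| 58 (no dropout) | 82.9% |

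Power is almost the same at 46 and 48 because the exact test changes in discrete steps.

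**Step 4: size, and a less conservative exact test.** At 48 per arm the maximum type I error of Fisher's test is 3.2%, well inside 5%. Boschloo's exact test uses the Fisher P value as its statistic but calibrates it so that the maximum size stays below 5%. At 25% vs 5% its power is 77.7% with 48 per arm (maximum size 4.9%) and 78.1% with 46 per arm (maximum size 4.7%).

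**The case against.** The strongest reply is that the shortfall rests on rates the plan does not state. It speaks of more conservative rates in the plural, so both arms may have moved. At about 22.5% vs 2.5%, Fisher's test has 80.8% power at 48 per arm, and the plan would agree with itself. Nor does the uncorrected formula at 25% vs 5% give exactly 48: it rounds up to 49. A one-sided formula with continuity correction does give 48 at that pair (47.8 before rounding). The effect is also bounded: with all 116 patients evaluable, power at 25% vs 5% is 82.9%, and at the cited 25% vs 0% it is about 99% with 48 per arm.

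Part of this stands. The pair is an inference, and the documents cannot exclude a lower one. The alternatives fit less well, though. A design built on Fisher's test at 22.5% vs 2.5% would not have needed 48, because that test already has 81.0% at 46 per arm. The one-sided route conflicts with the plan's own two-sided threshold. The 82.9% requires no dropout, while the plan anticipates 20%. The 99% is for a 25-point gap, not the 20 points on which the trial is sized.

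It is also fair to say that Boschloo's test is not required to correct the omission: Fisher's test is valid and prespecified, and Boschloo's stays short of 80% here. It is an option, not a necessity.

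**Conclusion.** The concern holds. The omission of the two design rates and the sizing method is certain. Across the 20-point pairs tabulated, the same statement is compatible with Fisher power from about 61% to about 94%.

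On the best-supported reading, 25% vs 5%, the stated 80% is too high by about 8 points. Power is 72.2% at 48 per arm and 72.1% at the roughly 46 per arm expected after dropout. This conclusion assumes that pair, an absolute difference, equal arms and a two-sided Fisher test at P < 0.05. At a C-SEMS rate of about 2.7% or less with the same gap, the stated power is right at 48 per arm. The problem lies in the power claim; the validity of the test is not in question.

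**What to change.** State both assumed failure rates and the sizing method, and report power for the test that will be used at the expected evaluable number.

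- **If the rates are 25% vs 5%**, either (a) keep Fisher's test and restate power as about 72%, or (b) prespecify Boschloo's exact test for the primary outcome and state about 78%. Boschloo's test keeps its maximum size below 5% and is never less powerful than Fisher's.
- **If a lower pair such as 22.5% vs 2.5% was used**, stating it is enough, with Fisher power of about 81%.

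The cost is wording only, with no added patients. At 25% vs 5% the plan must accept a less favourable power figure, and even option (b) stays about 2 points below 80%. Option (b) also replaces a familiar primary test with a less familiar one.

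### The enrolment target of 116 does not cover the stated 20% loss: 96 evaluable patients would need 120 randomised, and 116 leaves about 92 or 93

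*Combined protocol and SAP*

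**What the plan says.** Everything relevant is in two consecutive sentences of the combined protocol and SAP, under the heading Sample size and planned statistical analysis.

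- **Requirement.** The plan says "a sample size of 96 patients (48 per treatment arm) would be required", and gives the purpose as "to detect a 20% difference in stent failure rates at 80% power with an alpha level of 0.05".
- **Loss and target.** It continues: "Also anticipating a 20% rate of dropout/loss to follow-up, the goal would be to enroll and randomize 116 total patients in the study".

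The same section cites local retrospective data showing a "long-term 25% failure rate of U-SEMS and 0% failure rate of C-SEMS" and says the trial assumes something more conservative. It does not give the two failure rates behind the 20-point difference. The document contains no inflation formula, no other definition of the dropout rate, no rule for replacing patients and no further allowance.

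**The concern.** Dropout happens to patients who have been randomised, so a 20% rate applies to the number randomised. To finish with 96, the number randomised must satisfy N × 0.80 = 96. The target of 116 does not. It looks like 20% of the required number added on top, which always gives too few.

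At stake is the consistency of the main sample-size statement. A trial that recruits in full and loses exactly the share it expects would still end below the number it calls required. The enrolment goal and the loss allowance are also figures that readers will use to judge whether the trial could answer its primary question.

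**Working it through.** **Inputs, all from the sample-size section**

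- Evaluable patients required: 96 (48 per arm)
- Anticipated dropout or loss: 20%
- Number to randomise: 116

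**1. Reproduce the plan's figure.** Multiply the requirement by (1 + loss):

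- Total: 96 × 1.20 = 115.2, rounded up to 116
- Per arm: 48 × 1.20 = 57.6, rounded up to 58, and 58 × 2 = 116

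Both routes give 116 exactly.

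**2. Find the number that covers a 20% loss.** Divide the requirement by (1 − loss):

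- Total: 96 / 0.80 = 120
- Per arm: 48 / 0.80 = 60

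Check: 120 × 0.80 = 96. The gap from the plan's target is 120 − 116 = 4 patients. Rounding does not explain it, because 96 / 0.80 is already a whole number.

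**3. Find what 116 leaves after a 20% loss.**

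- Total: 116 × 0.80 = 92.8, so 92 or 93 patients
- Per arm: 58 × 0.80 = 46.4, so about 46
- Shortfall: 96 − 93 = 3 to 96 − 92 = 4 patients

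**4. Find the loss that 116 can bear.** 1 − 96/116 = 0.172, or 17.2%.

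Steps 1 to 4 use only figures the plan states.

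**5. Effect on power.** This step needs the two failure rates, which the plan does not give. I assume 25% v 5%, which keeps the retrospective U-SEMS rate and the 20-point difference, and show alternatives below. With a two-sided alpha of 0.05 and the pooled normal approximation, power = Φ[(difference − 1.96 × SE under the null) / SE under the alternative], where

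- SE under the null = √[2 × 0.15 × 0.85 / n]
- SE under the alternative = √[(0.25 × 0.75 + 0.05 × 0.95) / n]

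The results are:

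- n = 48 per arm: (0.20 − 1.96 × 0.0729) / 0.0700 = 0.817, power 79.3%
- n = 46 per arm: (0.20 − 1.96 × 0.0745) / 0.0715 = 0.757, power 77.5%

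At these rates the pooled formula asks for 49 per arm and the unpooled formula for 47. Both are close to the stated 48, so the assumption is plausible, but it is not confirmed.

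Power over a range of assumptions:

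| Assumed rates | Method | 48 per arm | 46 per arm |
|---|---|---|---|
| 25% v 5% | Pooled normal | 79.3% | 77.5% |
| 25% v 5% | Unpooled normal | 81.6% | 79.9% |
| 25% v 5% | Fisher's exact | 72.2% | 72.1% |
| 24% v 4% | Pooled normal | 81.6% | 80.0% |
| 22% v 2% | Pooled normal | 86.6% | 85.1% |
| 22% v 2% | Fisher's exact | 83.0% | 82.9% |

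In every row the cost of the shortfall is under 2 percentage points. Under Fisher's exact test, which the plan names for the primary comparison, it is about 0.1 point.

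**The case against.** The strongest reply is that this is bookkeeping. Four patients change no design decision, and the loss of power under the planned test is about a tenth of a point. That is right about the consequence, and nothing here claims more. It does not make the figure correct.

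A second reply is that the power figures rest on rates the plan never states. This also stands. At 46 per arm, power can fall below 80% or stay above it depending on the rates and formula chosen, so the shortfall does not by itself show that 80% power is lost. It shows only that 96, 20% and 116 disagree, and that finding needs no failure rates.

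A third is that the 20% might have been meant as a share of 96. The plan gives no such definition, and it ties the rate to the number to enrol and randomise. Loss can only arise among those patients.

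A fourth is that some patients lost late may still contribute an outcome, since follow-up uses record review or patient self-report and no analysis population is defined. That is possible in practice. But the plan's own allowance only makes sense if lost patients drop out of the evaluable count, and the 92.8 above uses the same convention.

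**Conclusion.** The concern holds. With 96 evaluable patients required and 20% lost, the matching enrolment target is 120. The stated 116 yields about 92 or 93 evaluable patients, roughly 46 per arm, and supports a loss of at most 17.2%. This rests only on the plan's own 96, 20% and 116, with lost patients counted as not evaluable, as the allowance implies.

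The practical effect is minor: 3 to 4 evaluable patients and, over the assumed rates examined, less than 2 points of power. It is still worth correcting, because the error is certain and sits in the main sample-size statement.

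**What to change.** Correct the sentence that sets the enrolment target, in one of two ways:

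- **Keep 116** and state that it allows for about 17% dropout or loss. This needs no further information.
- **Keep 20%** and state that 116 yields about 46 evaluable patients per arm, with power restated at that size. The sponsor should then also state the two failure rates and the formula used, since power cannot be recalculated without them.

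If both 96 and 20% are to stand, the target that matches them is 120, at a cost of 4 more patients. Either of the two wording changes costs one sentence and no patients.
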